6 OBJECTIVES AND ENDPOINTS

6.1 Primary Objective

The primary objective of this study is to evaluate the safety of the Omnipod Horizon™ CGM-informed bolus calculator in patients with type 1 diabetes during Manual Mode operation.

6.1.1 Primary Endpoints

The primary objective will be to evaluate the safety of the CGM-informed bolus calculator using the following endpoints as measured by the system:

Glucose metrics during the 4-hour post bolus period from Phase 2 will be compared to Phase 1:

- % of time < 70 mg/dL
- % of time > 180 mg/dL

6.2 Secondary Objective

The secondary objective of this study is to evaluate additional glycemic measures of effectiveness of the Omnipod Horizon™ CGM-informed bolus calculator during Manual Mode operation.

6.2.1 Secondary Endpoints

The secondary objective will be evaluated using the following per subject effectiveness endpoints:

Glucose metrics during the 4-hour post bolus from Phase 2 will be compared to Phase 1:

- Mean glucose
- % of time < 54 mg/dL
- % of time \geq 250 mg/dL
- % of time \geq 300 mg/dL
- % of time in range 70-180 mg/dL

Glucose metrics from Phase 2 will be compared to Phase 1, during the day (6AM up to 12AM), overnight (12AM up to 6AM), and overall:

- Mean glucose
- % of time < 54 mg/dL
- % of time < 70 mg/dL
- % of time > 180 mg/dL
- % of time \geq 250 mg/dL
- % of time \geq 300 mg/dL
- % of time in range 70-180 mg/dL
- % of time in range 70-140 mg/dL
- Standard deviation

- Coefficient of variation

7 SUBJECT SELECTION AND ELIGIBILITY

Potential subjects for this study will include individuals who have been diagnosed with type 1 diabetes for at least 6 months and are current or prior Omnipod users. Subjects aged 6-70 from the Omnipod Horizon™ Pivotal Study (G190270) may participate in this study during the study pause and must complete this study prior to their recommencement of the pivotal study. Subjects aged 2-5.9 may be recruited from the pivotal study but must complete or withdraw from this study before commencement of the Standard Therapy phase of the preschool pivotal study. Potential subjects will be selected at each clinical study site and screened accordingly. Every effort will be made to establish eligibility of the patient prior to enrollment. Only patients who appear to meet all eligibility criteria will be enrolled in the study. Subject eligibility will be confirmed by study staff during a screening visit. A point of care (POC) A1C will be used at screening to determine eligibility.

7.1 Visit 1

Visit 1 will be conducted either over the telephone or in person at the clinical study site. This visit will assess subject's eligibility and will include:

- Signing of informed consent/assent
- Review of inclusion/exclusion criteria
- Screening assessments performed following Table 1: Schedule of Assessments

Informed Consent

Subjects who appear to meet the eligibility criteria will be asked to sign an Informed Consent Form (ICF) approved by each respective Institutional Review Board (IRB) for participation in the study prior to completing any screening assessments. A parent/guardian must sign the ICF for subjects <18 years of age. Assent will be obtained from subjects aged <18 years per State requirements. Failure to provide informed consent/assent will render the subject ineligible for the study. Due to utilizing screening assessments for subjects aged 6-70 years that are participating in the Omnipod Horizon™ Pivotal Study, the date of consent for this study will occur much later than the date of the screening assessments.

Due to restrictions in place for the COVID-19 pandemic, sites may perform the informed consent process over the telephone per their site's procedures.

Subjects must also have a signed HIPAA (Health Insurance Portability and Accountability Act) release of protected health information (PHI). The release may be a stand-alone document or part of the informed consent.

After informed consent/assent is obtained, a subject identification number will be issued to uniquely identify each subject. The unique identifier will be used to identify the subject throughout the study and will be used for all source documents and electronic Case Report Forms (eCRFs). If the subject is also participating in

the Omnipod Horizon™ Pivotal Study, they may retain their same subject identification number for both studies.

Inclusion Criteria

Subjects must meet all the following criteria in order to be enrolled in the study:

1. Age at time of consent/assent 2-70 years
2. Subjects aged < 18 years must be living with parent/legal guardian
3. Diagnosed with type 1 diabetes for at least 6 months. Diagnosis is based on investigator's clinical judgment
4. Must be a current Omnipod user, or have used an Omnipod in the past
5. Investigator has confidence that the subject, parent, or legal guardian, can successfully operate all study devices and can adhere to the protocol
6. Willing to use only the following types of Insulin during the study: Humalog, Novolog, Admelog, or Apidra
7. Must be willing to use the Omnipod Horizon™ in Manual Mode only and agree not to use Automated Mode functionality
8. Must be willing to use the Omnipod Horizon™ bolus calculator without a connected CGM for the first 7-days of Manual Mode (Phase 1) while manually entering BG values to deliver boluses
9. Must be willing to use the Omnipod Horizon™ bolus calculator with a connected CGM for the last 7-days of Manual Mode (Phase 2) using the CGM-informed bolus calculator to deliver boluses
10. Willing to wear the system continuously throughout the study
11. For subjects not currently enrolled in the Omnipod Horizon™ Pivotal Study (G190270), A1C <10%
12. Must be willing to use the Dexcom App on the Omnipod Horizon™ PDM as the sole source of Dexcom data (except for the Dexcom Follow App)
13. Able to read and speak English fluently (if subject is a young child then Caregiver must meet the criteria)
14. Willing and able to sign the Informed Consent Form (ICF) and/or has a parent/guardian willing and able to sign the ICF. Assent will be obtained from subjects aged <18 years per State requirements.
15. For subjects aged 2-5.9 years of age, parents or trained caregivers agree to be physically present during the decision and delivery of insulin boluses for this age group, as well as agree to be available for glucose monitoring and treatment during the 4-hour post bolus period.

Exclusion Criteria

Subjects who meet any of the following criteria will be excluded from the study:

1. A medical condition, which in the opinion of the investigator, would put the subject at an unacceptable safety risk
2. History of severe hypoglycemia in the past 6 months
3. History of DKA in the past 6 months, unrelated to an intercurrent illness or infusion set failure
4. Plans to receive blood transfusion over the course of the study
5. Currently diagnosed with anorexia nervosa or bulimia

6. Acute or chronic kidney disease or currently on hemodialysis
7. History of adrenal insufficiency
8. Has taken oral or injectable steroids within the past 8 weeks or plans to take oral or injectable steroids during the study
9. Unable to tolerate adhesive tape or has any unresolved skin condition in the area of sensor or pump placement
10. Plans to use insulin other than U-100 insulin intended for use in the study device during the study
11. Use of non-insulin anti-diabetic medication other than metformin (e.g. GLP1 agonist, SGLT2 inhibitor, DPP-4 inhibitor, pramlintide)
12. Current or known history of coronary artery disease that is not stable with medical management, including unstable angina, or angina that prevents moderate exercise despite medical management, or a history of myocardial infarction, percutaneous coronary intervention, or coronary artery bypass grafting within the previous 12 months
13. Clinical signs of hypothyroidism and hyperthyroidism
14. Pregnant or lactating, or is a woman of childbearing potential and not on acceptable form of birth control (acceptable includes abstinence, condoms, oral/injectable contraceptives, IUD or implant)
15. Currently participating or plans to participate in another clinical study using an investigational drug or device other than Omnipod Horizon™. Subjects may be recruited from the Omnipod Horizon™ Pivotal Study (G190270).
16. Unable to follow clinical protocol for the duration of the study or is otherwise deemed unacceptable to participate in the study per the investigator's clinical judgment

Screening Assessments

Subjects who appear to meet the eligibility criteria and have signed the informed consent will continue to the screening visit which will be performed either over the phone (for subjects currently enrolled in the Omnipod Horizon™ Pivotal Study (G190270) or at the clinical study site.

Screening assessments must be completed within 30 days prior to the Phase 1 start date (assessments do not need to but may be completed on the same day). The assessments will include:

- Medical history (including prior and current medical conditions and surgical history)*
- Demographics (age, gender, race)
- Point of care A1C*
- Pregnancy test for women of childbearing potential
- Review of concomitant medications
- Height (if visit is conducted in person at the clinical study site)*
- Weight (if visit is conducted in person at the clinical study site)*
- Vital signs (if visit is conducted in person at the clinical study site)*

*For subjects currently enrolled in the Omnipod Horizon™ Pivotal Study (G190270), specified screening assessments are not required if they were done for the Pivotal study, and there are no significant changes from the Pivotal study screen

assessments. For subjects aged 2-5.9 that plan to participate in the Pivotal study, the specified screening assessments only need to be collected once, as long as they are completed within the timeframe required by both studies.

8 OMNIPOD HORIZON™ MANUAL MODE

The Omnipod Horizon™ Manual Mode will consist of two outpatient phases:

1. 7 days of Omnipod Horizon™ use in Manual Mode without a connected CGM using manual entry of BG values to deliver boluses (Phase 1) followed by;
2. 7 days of Omnipod Horizon™ use in Manual Mode with a connected CGM using the CGM-informed bolus calculator to deliver boluses (Phase 2)

Enrollment

Subjects who meet all eligibility criteria and have completed all screening assessments will continue to enrollment. A subject is enrolled in the study at the commencement of Visit 2. Subjects that do not meet the eligibility criteria will not continue in the study and will be considered screen failures.

If for any reason a subject is no longer eligible for the study before enrollment, the subject will not continue in the study. No additional study assessments will be required. The reason for study exit will be clearly documented.

8.1 Phase 1

8.1.1 Visit 2

Visit 2 represents the commencement of the first 7 days of Manual Mode (Phase 1) and will be conducted either over the telephone or in person at the clinical study site on Day 1. This visit will include:

- Review of concomitant medications
- Assessment of adverse events
- Training on Glucagon administration and information on treatment of hypo/hyperglycemia (if training was not previously performed while participating in the Omnipod Horizon™ Pivotal Study (G190270)
- Study device training per manufacturer's instructions (BG and ketone meters), (if training was not previously performed while participating in the Omnipod Horizon™ Pivotal Study (G190270)
- Omnipod Horizon™ System device training conducted by trained clinical site staff (if training was not previously performed while participating in the Omnipod Horizon™ Pivotal Study (G190270)
 - Subjects will be trained on operating Omnipod Horizon™ in Manual Mode.
 - This will include first time device set-up with entry of basal profile, bolus calculator settings with insulin:carbohydrate ratio, target

glucose and correction factor. Subjects should enter settings similar to their usual settings as appropriate.

- The Pod will be filled with the subject's own U-100 rapid-acting insulin and placed on body.
- Subjects will also be trained on use of Dexcom G6 CGM, setting up low (recommended to be 70 mg/dL or higher) and high glucose alerts (recommended to be 300 mg/dL or lower), setting up Dexcom Follow as desired, and calibrating their CGM as required, per the manufacturer's instructions
- Subjects will be trained to use the Bolus Calculator, entering in estimated carbs for meals and manually entering a BG value
- Subjects may choose their desired target BG ranging between 110-150 mg/dL in increments of 10 mg/dL for the bolus calculator

- Dispense Omnipod Horizon™ System, including CGM (if System was not previously dispensed while participating in the Omnipod Horizon™ Pivotal Study (G190270))
- QC testing of BG and ketone meter (if devices were not previously dispensed while participating in the Omnipod Horizon™ Pivotal Study (G190270))
 - Must pass as least one level of quality control testing prior to dispensing. QC testing may occur at any time prior to dispensing to subject.
- Removal of the subject's personal insulin pump (if not currently using the Omnipod Horizon™ System in Manual Mode)
 - Investigators should use the Insulet-provided Patient Therapy Order Form (PTOF) to document pump settings (Appendix A)
- Placement of the Omnipod Horizon™ on body (if not currently using the Omnipod Horizon™ System in Manual Mode)
- CGM sensor placement (if not currently wearing Omnipod Horizon™ study CGM)
 - Approved anatomical locations for CGM sensor placement will be reinforced as well as the importance of using approved locations
- Assessment of complaints and/or device deficiencies
- Each subject will initiate their treatment marking their commencement of the first 7 days of Manual Mode (Enrollment and Phase 1).

Subjects will be dispensed the following devices and supplies (if not currently enrolled in the Omnipod Horizon™ Pivotal Study (G190270)):

- Omnipod Horizon™ PDM and Pods
- Dexcom transmitter
- Dexcom sensors
- Contour® Next One blood glucose meter
- Contour® Next One blood glucose meter test strips
- Lancets
- Precision Xtra blood ketone meter
- Precision Xtra blood ketone meter test strips

During the first 7 days of Manual Mode, subjects will be instructed to:

- Use the bolus calculator to administer meal boluses for all meals when carbohydrates are consumed as well as to administer correction boluses, when desired. For meal boluses, subjects will estimate the grams of carbohydrates for each meal, enter the carbohydrate estimate into the bolus calculator, check and manually enter their BG value into the bolus calculator and administer their meal bolus. For correction boluses, subjects will check and enter their BG value into the bolus calculator and administer their correction bolus. The timing of the bolus delivery will be per each subject's typical dosing routine.
- Consume meals and snacks of their own choosing.
- Subjects may adjust their basal rates or use advanced features such as Temp Basal and Extended Bolus per usual
- Follow their pre-exercise management such as insulin reduction for meal boluses, consumption of snacks, or adjusting their insulin delivery settings
- Treat themselves per their usual routine if they become hypoglycemic or hyperglycemic or have symptoms of either at any time during the study
- Change their CGM per manufacturer's instructions or sooner if necessary
- Change the Pod at least once every 72 hours
- For subjects aged 2-5.9 years of age, parents or trained caregivers will be instructed that they need to be physically present during the decision and delivery of insulin boluses for this age group, as well as be available for glucose monitoring and treatment during the 4-hour post bolus period.

Subjects and caregivers will be reminded to NOT use the system in Automated Mode for the duration of the 14-day study. Any use of automated mode will be considered a protocol deviation.

Subjects not currently enrolled in the Omnipod Horizon™ Pivotal Study (G190270) will be provided, by the site, information regarding treatment of hypoglycemia and hyperglycemia including sick day management and emergency management of severe hypoglycemia and diabetic ketoacidosis. Instructions will be given to subjects on how to contact clinical study staff 24-hours per day to report any study related problems. Subjects will be encouraged to call the clinical study site at any time with any concerns.

8.1.2 Visit 3

Visit 3 will be conducted either over the telephone or in person at the clinical study site on Day 3 ±1d. This visit will include:

- Review of concomitant medications
- Assessment of adverse events
- Assessment of complaints and/or device deficiencies
- Data review by clinician to ensure that subject is delivering boluses as instructed during Visit 2

8.2 Phase 2

8.2.1 Visit 4

Visit 4 will be conducted either over the telephone or in person at the clinical site on Day 8 ± 1 d. This visit will mark the start of Phase 2, which is 7-days of Manual Mode with a connected CGM using the CGM-informed bolus calculator to deliver boluses. This visit will include:

- Review of concomitant medications
- Assessment of adverse events
- Pairing the CGM transmitter to the Horizon App on the PDM
- Assessment of complaints and/or device deficiencies
- Data review by clinician to ensure that subject was delivering boluses as instructed during Visit 2.
- Upload BG and ketone meter data (if visit is conducted in person at the clinical study site)

During this visit subjects will be instructed to:

- Use the CGM-informed bolus calculator to administer meal boluses for all meals when carbohydrates are consumed as well as to administer correction boluses, when desired. For meal boluses, subjects will estimate the grams of carbohydrates for each meal, enter the carbohydrate estimate into the bolus calculator, choose 'Enter CGM' to populate the bolus calculator and administer their meal bolus. For correction boluses, subjects will choose 'Enter CGM' to populate the bolus calculator and administer their correction bolus. The timing of the bolus delivery will be per each subject's typical dosing routine.
- Consume meals and snacks of their own choosing.
- Subjects may adjust their basal rates or use advanced features such as Temp Basal and Extended Bolus per usual
- Follow their pre-exercise management such as insulin reduction for meal boluses, consumption of snacks, or adjusting their insulin delivery settings
- Treat themselves per their usual routine if they become hypoglycemic or hyperglycemic or have symptoms of either at any time during the study
- Change their CGM per manufacturer's instructions or sooner if necessary
- Change the Pod at least once every 72 hours
- For subjects aged 2-5.9 years of age, parents or trained caregivers will be instructed that they need to be physically present during the decision and delivery of insulin boluses for this age group, as well as be available for glucose monitoring and treatment during the 4-hour post bolus period.

8.2.2 Visit 5

Visit 5 will be conducted either over the telephone or in person at the clinical study site on Day 10 ± 1 d. This visit will include:

- Review of concomitant medications

- Assessment of adverse events
- Assessment of complaints and/or device deficiencies
- Data review by clinician to ensure that subject is delivering boluses as instructed during Visit 4

8.2.3 Visit 6 (End of Study)

Visit 6 will be conducted either over the telephone or in person at the clinical study site on Day 14 ±1d. This visit will include:

- Review of concomitant medications
- Assessment of vital signs (if visit is conducted in person at the clinical study site)
- Assessment of adverse events
- Return of devices (if not commencing or recommencing their participation in the Omnipod Horizon™ Pivotal Study (G190270). Subjects aged 2-5.9 may hold onto their devices if continuing onto the Pivotal study, but must return to using their standard therapy for the Pivotal study Standard Therapy Phase.)
- Assessment of complaints and/or device deficiencies
- Data review by clinician to ensure that subject was delivering boluses as instructed during Visit 4
- Upload BG and ketone meter data (if visit is conducted in person at the clinical study site)

This visit will mark the end of this study for each subject.

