10.3.2 Reportable Adverse Events

Adverse events will be assessed on an ongoing basis throughout the study. Adverse event reporting will begin at the time of enrollment (i.e., insertion of the CGM sensor) and continue until the subject's participation has ended. All adverse events must be followed until resolution, or until the AE has stabilized, or until the study has been completed.

Pre-existing medical conditions or symptoms observed prior to enrollment will not be recorded as an AE and should be collected in the subject's medical history. In the event there is a change (i.e., worsening) in the pre-existing medical condition or symptoms after enrollment meeting the criteria of a reportable adverse event, then an AE must be reported.

For this protocol, a reportable adverse event includes any untoward medical occurrence that meets one of the following criteria:

1. An SAE
2. An ADE unless excluded from reporting in Hypoglycemic Events and Hyperglycemic/Ketotic Events sections below
3. An AE occurring in association with a study procedure
4. An AE not related to a study device issue which leads to temporary or permanent discontinuation of the study device
5. An AE that affects the participant's ability to complete any study procedures
6. An AE for which a visit is made to a hospital emergency department
7. Hypoglycemic Events as defined below
8. Hyperglycemia/Ketotic Events as defined

Skin reactions from sensor or pod placement are only reportable if severe and/or required treatment.

For the purpose of this protocol, mild symptoms of hypoglycemia and hyperglycemia (i.e., clinically non-significant) or blood glucose values out of the normal range (whether or not they resulted in delayed meals or correction boluses) will not be reported as AEs unless determined to meet the reportable criteria in the Hypoglycemic Events and Hyperglycemic/Ketotic Events sections below.

All reportable AEs—whether volunteered by the participant, discovered by study personnel during questioning, or detected through physical examination, laboratory test, or other means—will be reported on an AE eCRF.

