11.6 Safety Analyses

11.6.1 Evaluation of Adverse Events

All adverse events reported over the course of the study will be summarized and tabulated by study phase, event category, seriousness, severity, and relationship to the study and the investigational device. For the purposes of summarization, an event will be considered “Related” if the relationship was deemed as “Possibly Related” or “Related”. In cases where the same event is reported more than once per subject, the event will only be counted once in the incidence table(s).

Adverse events leading to death or to discontinuation from the study will be listed separately. A listing of all adverse events will be provided.

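### Nominal visit days give Phase 2 about one day less follow-up than Phase 1, and the by-phase event tables carry no exposure time

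*Combined protocol and SAP*

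**What the plan says.** Section 8.1.1 starts Phase 1 at Visit 2, which "will be conducted either over the telephone or in person at the clinical study site on Day 1", with no window. Section 8.2.1 sets the switch: "Visit 4 will be conducted either over the telephone or in person at the clinical site on Day 8 ± 1 d". It adds: "This visit will mark the start of Phase 2, which is 7-days of Manual Mode with a connected CGM". Section 8.2.3 sets the last visit: "Visit 6 will be conducted either over the telephone or in person at the clinical study site on Day 14 ±1d". It then states: "This visit will mark the end of this study for each subject". Table 1 carries the same days and windows.

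Under Section 10.3.2, adverse event reporting runs from enrolment until participation ends. Section 8 places enrolment at the start of Visit 2.

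On analysis, Section 11.6.1 says: "All adverse events reported over the course of the study will be summarized and tabulated by study phase". Section 11.6.2 treats device deficiencies in a similar way. Section 11.1 makes unique subjects the default denominator for percentages, and Section 11.4.1 bases these safety analyses on the ITT set. No section mentions subject-days, an event rate or the observed length of each phase. Section 11.4.3 defines the per-protocol set by 80% system use in Phase 2, which it equates with about 5.6 days.

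**The concern.** The two phases are presented as matched weeks, but the visit days that bound them are not equally spaced. Events can be recorded only between Visit 2 and Visit 6, and Visit 4 divides that interval. If Phase 2 is observed for less time, its event and device-deficiency counts tend to be lower for a reason unrelated to the calculator. Phase 2 is the tested use and safety is the primary objective, so on nominal days the imbalance favours the product. Because no exposure time is planned for the tables, a reader cannot correct for it.

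The per-protocol rule raises a related problem. Its 5.6-day figure presupposes a 7-day Phase 2, which the nominal visit days do not deliver in elapsed time.

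**Working it through.** **Inputs.** Visit 2 = Day 1 (8.1.1). Visit 4 = Day 7, 8 or 9 (8.2.1). Visit 6 = Day 13, 14 or 15 (8.2.3). Stated length of each phase: 7 days. Planned evaluable subjects: 30 (11.2). The plan contains no power calculation to reproduce.

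**The plan's own figure.** 0.80 × 7 = 5.6 days, so the per-protocol threshold assumes a 7-day Phase 2.

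**Nominal elapsed time**, with visits at a similar clock time:
- Phase 1 = Visit 4 − Visit 2 = 8 − 1 = 7 days (168 h)
- Phase 2 = Visit 6 − Visit 4 = 14 − 8 = 6 days (144 h)
- Ratio = 6/7 = 0.857, or 14.3% less

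**All nine whole-day in-window combinations, elapsed days:**

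| Visit 4 | Visit 6 | Phase 1 | Phase 2 | Phase 2 v Phase 1 |
|---|---|---|---|---|
| 7 | 13 | 6 | 6 | equal |
| 7 | 14 | 6 | 7 | longer |
| 7 | 15 | 6 | 8 | longer |
| 8 | 13 | 7 | 5 | shorter |
| 8 | 14 | 7 | 6 | shorter |
| 8 | 15 | 7 | 7 | equal |
| 9 | 13 | 8 | 4 | shorter |
| 9 | 14 | 8 | 5 | shorter |
| 9 | 15 | 8 | 6 | shorter |

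Phase 2 is shorter in 5, equal in 2 and longer in 2. It reaches 7 elapsed days in 3 of 9, and never after a Day 9 Visit 4.

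**Alternative convention: inclusive calendar days.** Phase 1 = Visit 4 − 1 and Phase 2 = Visit 6 − Visit 4 + 1. Nominal days give 7 and 14 − 8 + 1 = 7. Across the nine combinations Phase 2 is shorter in 4, equal in 1 and longer in 4.

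**Effect on event counts.** On nominal days, 30 subjects give 30 × 7 = 210 subject-days in Phase 1 and 30 × 6 = 180 in Phase 2. The documents give no event rate, so I assume a range, the same in both phases, with Poisson counts. The chance that a subject has at least one event is 1 − exp(−rate × days).

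| Assumed events per subject-day | Expected events, Phase 1 v 2 | Subjects with an event, Phase 1 v 2 | P(Phase 2 count lower) | P(Phase 2 count higher) |
|---|---|---|---|---|
| 0.005 | 1.05 v 0.90 | 3.4% v 3.0% | 0.384 | 0.304 |
| 0.01 | 2.1 v 1.8 | 6.8% v 5.8% | 0.454 | 0.338 |
| 0.02 | 4.2 v 3.6 | 13.1% v 11.3% | 0.513 | 0.345 |
| 0.05 | 10.5 v 9.0 | 29.5% v 25.9% | 0.589 | 0.325 |

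**Effect on the per-protocol threshold.** On 6 elapsed days, 80% is 0.80 × 6 = 4.8 days, while 5.6 days is 5.6/6 = 93%. In the three combinations with a 4- or 5-day Phase 2, 5.6 days cannot be reached.

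**The case against.** The documents plainly intend seven days each, and inclusive counting (Days 1–7 and 8–14) gives that on nominal dates. Visit 6 may be a telephone call and no clock time is set, so a loss of a full 24 hours is an assumption. This stands in part. But the inclusive count yields seven full days only if observation runs to the end of Day 14, and Section 8.2.3 ends the study at the visit. Under that convention the phases still match in only 1 of 9 in-window combinations.

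A reader might infer that Phase 2 must record fewer events by construction. The documents do not support that. Phase 2 is as long as or longer than Phase 1 in 4 of 9 combinations. Even on nominal days the deficit is an expectation, and in the illustration above the Phase 2 count is the higher one with probability 0.304 to 0.345.

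A reader might also infer that the glucose comparison is distorted, or that losing a matched week biases it. Section 11.5.1 defines the percentage-of-time endpoints over evaluable CGM records, so shorter follow-up does not shift them mechanically. The documents show no weekday effect.

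The practical effect on the tables is also limited. Reportable events are narrow (10.3.2 to 10.3.4), many device issues are excluded (10.4), repeated events count once per subject in the incidence tables, and all adverse events are listed. No test between phases is specified for them, and the study is not powered. This limits the importance of the point but does not supply the missing denominator.

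**Conclusion.** The point holds as a modest defect in scheduling and reporting. The stated 7 days of Phase 2 do not agree with the Visit 4 and Visit 6 days in elapsed time (7 v 6 nominally, 6 to 8 v 4 to 8 within windows). The phases are unequal in 7 of 9 in-window combinations by elapsed days and in 8 of 9 by inclusive days. At equal rates on nominal days, expected Phase 2 events are about 14% lower. The percentages of subjects with an event differ by a little less than that in relative terms at the higher assumed rates.

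The 7 v 6 figure assumes visits at a similar clock time. The tallies count whole days and say nothing about how often each combination will occur. The event rates are assumed. One factor points the same way: if the ITT denominator is used for both phases, a subject who leaves during Phase 1 stays in the Phase 2 denominator while contributing no Phase 2 time.

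**What to change.** 1. In 11.6.1 and 11.6.2, add subject-days for each phase, and adverse events and device deficiencies per subject-day, beside the planned counts. Compute exposure from each subject's actual Visit 2, Visit 4 and Visit 6 (or withdrawal) times. This allows for unequal phase lengths whatever the visit dates, and for subjects who never enter Phase 2.
2. Reconcile the stated 7 days of Phase 2 with the Visit 4 and Visit 6 days in Table 1 and Section 8.2. State the counting convention, and align the 5.6-day figure in 11.4.3 with the result.
3. Set the Visit 6 window from the subject's actual Visit 4 instead of Day 1, so that an early or late switch does not change the planned length of Phase 2.

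The first change costs a few table columns. The third is a scheduling edit. If seven elapsed days are meant, Visit 6 would nominally move from Day 14 to 8 + 7 = Day 15, and to 9 + 7 = Day 16 after a Day 9 Visit 4. That is one or two days later than the present nominal day, and it delays some subjects' move to the pivotal study by the same amount.
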